6.5.4.3 Urinalysis

Not applicable

6.5.5 Electrocardiogram (ECG)

ECG measurements are not required per protocol but are recommended as part of the patient's Standard of Care.

6.5.6 Pregnancy and assessments of fertility

All pre-menopausal women who are not surgically sterile will have urine pregnancy tests performed locally at Visits 1, 5, 6, 7 and 8 and serum pregnancy tests performed locally at Visit 1 and the End of Study visit (Visit 9). A positive urine pregnancy test at Visit 1 constitutes a screen failure unless the serum β -hCG test is performed and found to be negative. In case of pregnancy discovered at any time during the open-label treatment period, the patient should be instructed to stop taking LCZ696 immediately. If the urine pregnancy test at Visit 6 or 8 is positive, LCZ696 must be stopped immediately. A follow-up serum pregnancy test can be performed at the discretion of the patient and investigator but restarting LCZ696 treatment can be considered only if the test is negative.

6.5.7 Appropriateness of safety measurements

The safety and clinical laboratory assessments performed in this study are similar to those used in the core study PARADIGM-HF (CLCZ696B2314). These assessments are appropriate for an investigational drug with the mechanism(s) of action of LCZ696 (angiotensin receptor antagonist and neprilysin inhibitor), the safety profile described in the LCZ696 Investigator Brochure, and the indication/patient population under study.

6.6 Other assessments

No additional tests will be performed on patients enrolled into this study.

7 Safety monitoring

7.1 Adverse events

All Adverse events reported will be recorded in the e-CRFs regardless of seriousness, causality, or actions (including angioedema-like events). An AE is any untoward medical occurrence (i.e., any unfavorable and unintended sign [including abnormal laboratory

findings], symptom or disease) in a subject or clinical investigation subject *after providing written informed consent* for participation in the study. Therefore, an AE may or may not be temporally or causally associated with the use of a medicinal (investigational) product.

The occurrence of adverse events should be sought by non-directive questioning of the patient at each visit during the study. Adverse events also may be detected when they are volunteered by the patient during or between visits or through physical examination, laboratory tests, or other assessments.

Abnormal laboratory values or test results constitute adverse events only if they fulfill at least one of the following criteria:

- they induce clinical signs or symptoms,
- they are considered clinically significant,
- they require therapy.

Clinically significant abnormal laboratory values or test results should be identified through a review of values outside of normal ranges/clinically notable ranges, significant changes from baseline or the previous visit, or values which are considered to be non-typical in patients with the underlying disease. Investigators have the responsibility of managing the safety of individual patients and identifying adverse events. Alert ranges for labs and other test abnormalities are included in Appendix 1.

Adverse events should be recorded in the Adverse Events CRF under the signs, symptoms or diagnosis associated with them accompanied by the following information.

- the severity grade
 - mild: usually transient in nature and generally not interfering with normal activities
 - moderate: sufficiently discomforting to interfere with normal activities
 - severe: prevents normal activities
- its relationship to the investigational treatment (no/yes)
- its duration (start and end dates) or if the event is ongoing an outcome of not recovered/not resolved should be reported.
- whether it constitutes an SAE
- action taken regarding investigational treatment
- whether other medication or therapies have been taken (concomitant medication/non-drug therapy)
- its outcome (not recovered/not resolved; recovered/resolved; recovering/resolving, recovered/resolved with sequelae; fatal; or unknown)

All adverse events should be treated appropriately. Treatment may include one or more of the following: no action taken (i.e. further observation only); investigational treatment dosage adjusted/temporarily interrupted; study drug(s) permanently discontinued; concomitant medication given; non-drug therapy given. The action taken to treat the adverse event should be recorded on the Adverse Event CRF.

Once an adverse event is detected, it should be followed until its resolution or until it is judged to be permanent, and assessment should be made at each visit (or more frequently, if necessary) of any changes in severity, the suspected relationship to the investigational study treatment, the interventions required to treat it, and the outcome.

The Sponsor may request additional information on specific adverse events of interest and may make requests to perform additional diagnostic tests to further assess the safety profile of the study medications. Such information may include diagnostic procedure reports, discharge summaries, autopsy reports, and other relevant information that may help in assessing the reported adverse event. All additional information will be de-identified prior to collection by Novartis or its agents.

Information about common side effects already known about the investigational drug can be found in the Investigator Brochure (IB) or will be communicated between IB updates in the form of Investigator Notifications. This information will be included in the patient informed consent and should be discussed with the patient during the study as needed.

The investigator should also instruct each patient to report any new adverse event (beyond the protocol observation period) that the patient, or the patient's personal physician, believes might reasonably be related to study treatment. This information should be recorded in the investigator's source documents, however, if the AE meets the criteria of an SAE, it must be reported to the Sponsor.

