7.2 Serious adverse events

7.2.1 Definition of SAE

An SAE is any adverse event with the appearance of (or worsening of any pre-existing) undesirable sign(s), symptom(s) or medical condition(s) which meets any one of the following criteria:

- is fatal or life-threatening
- results in persistent or significant disability/incapacity
- constitutes a congenital anomaly/birth defect
- requires inpatient hospitalization or prolongation of existing hospitalization, unless hospitalization is for:
 - routine treatment or monitoring of the studied indication, not associated with any deterioration in condition
 - elective or pre-planned treatment for a pre-existing condition that is unrelated to the indication under study and has not worsened since signing the informed consent
 - treatment on an emergency outpatient basis for an event not fulfilling any of the definitions of a SAE given above and not resulting in hospital admission
 - social reasons and respite care in the absence of any deterioration in the patient's general condition
- is medically significant, i.e. defined as an event that jeopardizes the patient or may require

medical or surgical intervention to prevent one of the outcomes listed above.

All malignant neoplasms will be assessed as serious under “medically significant” if other seriousness criteria are not met.

Life-threatening in the context of an SAE refers to a reaction in which the patient was at risk of death at the time of the reaction; it does not refer to a reaction that hypothetically might have caused death if more severe (see [Annex IV, ICH-E2D Guideline](#)).

Medical and scientific judgment should be exercised in deciding whether other situations should be considered serious reactions, such as important medical events that might not be immediately life threatening or result in death or hospitalization but might jeopardize the patient or might require intervention to prevent one of the other outcomes listed above. Examples of such events are intensive treatment in an emergency room or at home for allergic bronchospasm, blood dyscrasias or convulsions that do not result in hospitalization or development of dependency or abuse (see [Annex IV, ICH-E2D Guideline](#)).

Any suspected transmission via a medicinal product of an infectious agent is also considered a serious adverse reaction.

Unlike routine safety assessments, SAEs are monitored continuously and have special reporting requirements; see [Section 7.2.2](#).

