7.3 Liver safety monitoring

To ensure patient safety and enhance reliability in determining the hepatotoxic potential of an investigational drug, a standardized process for identification, monitoring and evaluation of liver events has to be followed.

Liver events are divided into two categories:

- Liver events of special interest (AESI) which consist of LFTs elevations
- Medically significant liver events which are considered as serious adverse events (SAEs) and which consist of marked elevations of LFTs and / or pre-specified adverse events.

Please refer to [Table 14-1](#) in Appendix 2 for complete definitions of liver events.

Any liver event which meets the criteria for "**medically significant**" event as outlined in [Table 14-1](#) of Appendix 2 should follow the **standard procedures for SAE reporting** as described in [Section 7.2.2](#).

Every liver event as defined in [Table 14-1](#) of Appendix 2 should be followed up by the investigator or designated personal at the trial site as summarized below. Detailed information is outlined in [Table 14-2](#) in Appendix 2.

- Repeating the LFT to confirm elevation as appropriate
- Discontinuation of LCZ696 if appropriate
- Hospitalization of the patient if appropriate

- A causality assessment of the liver event via exclusion of alternative causes (e.g., disease, co-medications)
- An investigation of the liver event which needs to be followed until resolution.

These investigations can include serology tests, imaging and pathology assessments, hepatologist's consultancy, based on the investigator's discretion. All follow-up information, and the procedures performed should be recorded on appropriate CRF pages, including the liver event overview CRF pages.

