SOLVD Investigators (1992) Effect of enalapril on mortality and the development of heart failure in asymptomatic patients with reduced left ventricular ejection fractions. *N Engl J Med*; 327:685-691.

13 Appendix 1: Clinically notable laboratory values

Clinically notable laboratory abnormalities for selected tests based on a percent change from baseline:

Hematology

RBC count	>50% increase, >20% decrease
Hemoglobin	>50% increase, >20% decrease
Hematocrit	>50% increase, >20% decrease
WBC count	>50% increase, >50% decrease
Platelet count	>75% increase, >50% decrease

Blood Chemistry

ALT (SGPT)	>150% increase
AST (SGOT)	>150% increase
BUN	>50% increase
Creatinine	>50% increase
Total bilirubin	>100% increase
CPK	>300% increase
Alkaline phosphatase	>100% increase
Sodium	>5% decrease
Potassium	>20% increase, >20% decrease
Uric acid	>50% increase

14 Appendix 2: Liver event and laboratory trigger definitions and follow-up requirements

Table 14-1 Liver event definitions

Definition/ threshold	
AE of special interest	
Laboratory values	ALT or AST > 3 x ULN ALP > 2 x ULN TBL > 1.5 x ULN
Medically significant event (SAE)	
Laboratory values	ALT or AST > 5 x ULN (with or without TBL > 2 x ULN [mainly conjugated fraction]) ALP > 5 x ULN (with or without TBL > 2 x ULN [mainly conjugated fraction]) TBL > 3 x ULN Potential Hy's Law cases (defined as ALT/AST > 3 x ULN and TBL > 2 x ULN [mainly conjugated fraction] without notable increase in ALP to > 2 x ULN)
AEs	Any clinical event of jaundice (or equivalent term) ALT or AST > 3 x ULN accompanied by general malaise, fatigue, abdominal pain, nausea, or vomiting, or rash with eosinophilia Any event that links to a preferred term (PT) in the MedDRA dictionary falling under the SMQ sub-module "Drug-related hepatic disorders – severe events only"** or any "Hy's law case" PT

* These events cover the following: hepatic failure, fibrosis and cirrhosis, and other liver damage-related conditions; the non-infectious hepatitis; the benign, malignant and unspecified liver neoplasms

Table 14-2 Liver event follow up requirements

Criteria	Event type	Actions required	Follow-up monitoring

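### Asymptomatic, untreated liver-test elevations, chiefly in the special-interest tier, may be recorded as AEs at one site and not at another, because Protocol 7.1 and Appendix 2 use different rules and neither is given precedence

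*Protocol*

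**What the plan says.** **General rule.** Protocol 7.1 states: "Abnormal laboratory values or test results constitute adverse events only if they fulfill at least one of the following criteria". The three criteria are alternatives: the value causes signs or symptoms, it needs therapy, or (the second in the list) "they are considered clinically significant". Significance is to be found by reviewing values outside normal or notable ranges, changes from baseline or the previous visit, and values untypical of the disease. The only list of limits that 7.1 cites is a different one from the liver tables: "Alert ranges for labs and other test abnormalities are included in Appendix 1".

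**Liver rule.** Protocol 7.3 sets up two categories. The lower is "Liver events of special interest (AESI) which consist of LFTs elevations". The upper is "Medically significant liver events which are considered as serious adverse events (SAEs) and which consist of marked elevations of LFTs", or certain pre-specified adverse events. Table 14-1 in Appendix 2 gives the lower limits as "ALT or AST > 3 x ULN ALP > 2 x ULN TBL > 1.5 x ULN". The corresponding isolated limits for the upper tier are ALT/AST above 5, ALP above 5 and bilirubin above 3 x ULN. None of these entries carries a symptom, judgement or therapy condition. In Table 14-2 the AESI rows are marked as applying to asymptomatic patients.

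**Entry on the AE page.** Protocol 6.5.4 requires entry when the abnormality causes symptoms or needs intervention and also meets the 7.1 criteria. It does not mention clinical significance as a separate route.

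**Data and analysis.** Protocol 8.3 keeps laboratory values in source documents and out of the clinical database. Protocol 9.4 and SAP 9.7.1.6.1 make overall AE and SAE frequencies part of the primary assessment.

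**The concern.** The study is descriptive and AE frequency is its main result, so the rule that decides what becomes an AE record matters more than usual. For liver tests there are two such rules. One depends on the investigator's view, and the other on a number. Neither refers to the other, and no order of precedence is given. Two sites could each follow the protocol, see the same asymptomatic value, and leave different records. The overall AE counts would then partly reflect site practice. Any omission would lower the counts.

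**Working it through.** No figure in the plan needs reproducing. The check sets the rules side by side and then asks whether Appendix 1, the one list that 7.1 cites, closes the gap.

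**Step 1: three asymptomatic, untreated cases**

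| Case | Appendix 2 | Protocol 7.1 | Protocol 6.5.4 |
|---|---|---|---|
| ALT 4 x ULN | AESI in both tables; investigator informs the sponsor | Symptom and therapy criteria fail; AE only if judged clinically significant | Entry not mandated |
| ALT 6 x ULN | SAE in Table 14-1; SAE report in Table 14-2 | Same judgement, but the protocol itself calls the event medically significant | Entry not mandated by the symptom/therapy sentence; a value that meets a seriousness category goes to SAE notification |
| Isolated ALP 6 x ULN | SAE in Table 14-1; in Table 14-2 an SAE report only if the elevation persists on repeat | As for ALT 6 x ULN | As for ALT 6 x ULN |

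In the first case the outcome rests entirely on one judgement. In the second, the protocol's own label goes most of the way to answering the question. In the third, the two liver tables also disagree with each other.

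**Step 2: does Appendix 1 bring the two rules together?** Appendix 1 flags a percentage rise from baseline, while Table 14-1 uses multiples of ULN. Let T be the Table 14-1 limit and p the Appendix 1 rise. A patient can exceed T without exceeding p when the baseline is above T / (1 + p).

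| Test | Appendix 1 rise | AESI limit reached un-flagged from baseline above | SAE limit reached un-flagged from baseline above |
|---|---|---|---|
| ALT/AST | >150% | 3 / 2.5 = 1.2 x ULN | 5 / 2.5 = 2.0 x ULN |
| ALP | >100% | 2 / 2 = 1.0 x ULN | 5 / 2 = 2.5 x ULN |
| Bilirubin | >100% | 1.5 / 2 = 0.75 x ULN | 3 / 2 = 1.5 x ULN |

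Exclusion criterion 10 admits ALT/AST up to 3 x ULN, so these baselines can occur. For example, ALT going from 1.5 to 3.5 x ULN is 3.5 / 1.5 - 1 = 133%. That is not notable in Appendix 1 but is an AESI in Table 14-1. ALT going from 2.5 to 5.1 x ULN is 5.1 / 2.5 - 1 = 104%, again not notable but above the Table 14-1 SAE limit. Any such value is outside the normal range, so 7.1 would still bring it up for review. Appendix 1 does not settle the outcome of that review.

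**Step 3: would the analysis show an omission?** SAP 9.7.1.6 limits the safety evaluation to adverse events and vital signs. SAP 9.7.1.3 mentions a safety laboratory evaluation, but none is specified and the values are not in the database. Protocol 7.3 sends follow-up information to liver event overview CRF pages, yet the SAP plans no table from them. An elevation absent from the AE page is therefore absent from every planned AE table.

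**Step 4: size.** The number missing would be 5,000 x r x s. Here r is the share of patients with an asymptomatic, untreated Appendix 2 elevation, and s is the share of those judged not clinically significant. The documents give neither r nor s.

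**The case against.** The strongest reply is that 7.1 and 7.3 can be read together. The clinical-significance criterion needs neither symptoms nor therapy. Protocol 7.2.1 counts medical significance as a seriousness criterion, Table 14-1 gives its upper tier that very label, and 7.3 requires those events to follow SAE reporting. On this reading 7.3 is the specific rule and 7.1 the general one.

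This largely stands for the SAE tier. A reader might infer that one value is necessarily an SAE in one section and no AE at all in another. The documents do not support that: it would take an investigator declaring insignificant what the protocol has declared medically significant. The reply does not reach the AESI tier, which has no such label and is written for asymptomatic patients.

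A reader might also infer that unrecorded events are lost. They are not. The liver CRF pages in 7.3 and the AESI rows of Table 14-2, which have the investigator report to the sponsor, leave a trace outside the AE page. What stands is that no planned table draws on that trace.

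Two further limits apply. The AESI tabulation in Protocol 9.4 and the SAP covers only hypotension, hyperkalemia and renal dysfunction, so it is unaffected. And 6.5.4 says when entry is required without saying that other entries are barred, so it leaves the gap open but does not forbid recording.

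**Conclusion.** The point holds as an inconsistency in a recording rule, mainly for asymptomatic, untreated elevations in the AESI tier: ALT/AST above 3 to 5, ALP above 2 to 5, and bilirubin above 1.5 to 3 x ULN. Whether these enter the overall AE counts depends on investigator judgement, although Appendix 2 classes them by number. The SAE tier is less exposed. Its clearest separate problem is isolated ALP above 5 x ULN, where Table 14-1 acts on the value and Table 14-2 on persistence.

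The conclusion assumes that no eCRF completion guide or other document outside the two reviewed settles the matter. It should not be turned into a patient count: multiplying 5,000 by assumed rates is tempting, but the documents offer no basis for them. No hypothesis test, error rate or sample size is involved. The effect is on the completeness and between-site consistency of AE counts, and it is worth correcting because the correction is cheap.

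**What to change.** - In Protocol 7.1, add that a laboratory value classed as a liver event in Appendix 2 counts as an adverse event and is entered on the Adverse Events eCRF.
- Align 6.5.4, so that its entry rule covers these values without requiring symptoms or therapy.
- Reconcile Tables 14-1 and 14-2 on isolated ALP above 5 x ULN (immediate or persistent elevation). Tie the SAE flag to Appendix 2 only after that, so that the recording rule does not choose between the tables by default.

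This takes a few lines in a protocol amendment and in the eCRF completion guide. The added recording rule itself changes no threshold, dose or stopping rule. The downside is a few more AE records, so liver event counts become slightly less favourable.

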7.2 Serious adverse events

7.2.1 Definition of SAE

An SAE is any adverse event with the appearance of (or worsening of any pre-existing) undesirable sign(s), symptom(s) or medical condition(s) which meets any one of the following criteria:

- is fatal or life-threatening
- results in persistent or significant disability/incapacity
- constitutes a congenital anomaly/birth defect
- requires inpatient hospitalization or prolongation of existing hospitalization, unless hospitalization is for:
 - routine treatment or monitoring of the studied indication, not associated with any deterioration in condition
 - elective or pre-planned treatment for a pre-existing condition that is unrelated to the indication under study and has not worsened since signing the informed consent
 - treatment on an emergency outpatient basis for an event not fulfilling any of the definitions of a SAE given above and not resulting in hospital admission
 - social reasons and respite care in the absence of any deterioration in the patient's general condition
- is medically significant, i.e. defined as an event that jeopardizes the patient or may require

medical or surgical intervention to prevent one of the outcomes listed above.

All malignant neoplasms will be assessed as serious under “medically significant” if other seriousness criteria are not met.

Life-threatening in the context of an SAE refers to a reaction in which the patient was at risk of death at the time of the reaction; it does not refer to a reaction that hypothetically might have caused death if more severe (see [Annex IV, ICH-E2D Guideline](#)).

Medical and scientific judgment should be exercised in deciding whether other situations should be considered serious reactions, such as important medical events that might not be immediately life threatening or result in death or hospitalization but might jeopardize the patient or might require intervention to prevent one of the other outcomes listed above. Examples of such events are intensive treatment in an emergency room or at home for allergic bronchospasm, blood dyscrasias or convulsions that do not result in hospitalization or development of dependency or abuse (see [Annex IV, ICH-E2D Guideline](#)).

Any suspected transmission via a medicinal product of an infectious agent is also considered a serious adverse reaction.

Unlike routine safety assessments, SAEs are monitored continuously and have special reporting requirements; see [Section 7.2.2](#).

7.2.2 SAE reporting

To ensure patient safety, every SAE, regardless of causality, occurring after the patient has provided informed consent and until 30 days following the last administration of study treatment must be reported to the Sponsor within 24 hours of learning of its occurrence. Any SAEs experienced after the 30 days period should only be reported to the Sponsor if the investigator suspects a causal relationship to study treatment.

Recurrent episodes, complications, or progression of the initial SAE must be reported as follow-up to the original episode, regardless of when the event occurs. This report must be submitted within 24 hours of the investigator receiving the follow-up information. An SAE that is considered completely unrelated to a previously reported one should be reported separately as a new event.

Information about all SAEs (either initial or follow up information) is collected and recorded in English on the paper Serious Adverse Event Report Form or the electronic Serious Adverse Event Form within the EDC system (where available). The investigator must assess the relationship to each specific component of the study treatment (if the study treatment consists of several components).

SAEs (initial and follow-up) that are recorded *on the paper SAE form* should be faxed within 24 hours of awareness of the SAE to the Sponsor’s local Drug Safety and Epidemiology Department. The telephone and fax number of the contact persons in the local department of Drug Safety and Epidemiology, specific to the site, are listed in the investigator folder provided to each site. The original copy of the SAE Report Form and the fax confirmation sheet must be kept with the case report form documentation at the study site. Follow-up

information should be provided using a new paper SAE Report Form stating that this is a follow-up to a previously reported SAE

SAEs (initial and follow-up) that are recorded *electronically* in the EDC system should be entered, saved and e-signed within 24 hours of awareness of the SAE or changes to an existing SAE. These data will automatically be submitted to the Sponsor's Drug Safety & Epidemiology immediately after investigator signature or 24 hours after entry, whichever occurs first.

Follow-up information provided should describe whether the event has resolved or continues, if and how it was treated, whether the treatment code was broken or not (not applicable in this study) and whether the patient continued or withdrew from study participation. Each re-occurrence, complication, or progression of the original event should be reported as a follow-up to that event regardless of when it occurs.

If the SAE is not previously documented in the Investigator's Brochure or Package Insert (new occurrence) and is thought to be related to the investigational treatment a Drug Safety and Epidemiology Department associate may urgently require further information from the investigator for Health Authority reporting. The Sponsor may need to issue an Investigator Notification (IN) to inform all investigators involved in any study with the same investigational treatment that this SAE has been reported. Suspected Unexpected Serious Adverse Reactions (SUSARs) will be collected and reported to the competent authorities and relevant ethics committees in accordance with Directive 2001/20/EC or as per national regulatory requirements in participating countries.

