7.6 Pregnancy reporting

In case a patient becomes pregnant, or plans to become pregnant, LCZ696 must be discontinued permanently. To ensure patient safety, each pregnancy occurring while the patient is on LCZ696 treatment must be reported to the Sponsor within 24 hours of learning of its occurrence. The pregnancy should be followed up to determine outcome, including spontaneous or voluntary termination, details of the birth, and the presence or absence of any birth defects, congenital abnormalities, or maternal and/or newborn complications.

Pregnancy should be recorded on a Clinical Trial Pregnancy Form and reported by the investigator to the Sponsor's local Drug Safety and Epidemiology Department. Pregnancy follow-up should be recorded on the same form and should include an assessment of the possible relationship to LCZ696 treatment.

Any SAE experienced during pregnancy must be reported on the SAE Report Form.

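### Protocol Sections 7.1 and 7.2.2 conflict on a new SAE more than 30 days after the last dose when the patient or personal physician, but not the investigator, suspects LCZ696

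*Protocol*

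**What the plan says.** Protocol Section 7.2.2 sets two regimes. From informed consent onward, every SAE is reportable whatever its cause, "until 30 days following the last administration of study treatment must be reported to the Sponsor within 24 hours of learning of its occurrence". After that the rule narrows: "Any SAEs experienced after the 30 days period should only be reported to the Sponsor if the investigator suspects a causal relationship". The same section keeps recurrences, complications and progression of an earlier SAE reportable at any time, as follow-up to that event.

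Protocol Section 7.1 closes with a separate instruction about new events "beyond the protocol observation period". The investigator is to ask each patient to report any such event that the patient or the patient's personal physician "believes might reasonably be related to study treatment". Non-serious events of this kind stay in the source documents; "however, if the AE meets the criteria of an SAE, it must be reported to the Sponsor". The sentence mentions neither the investigator's view of causality nor Section 7.2.2.

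Protocol Section 7.6 adds, for pregnancies: "Any SAE experienced during pregnancy must be reported on the SAE Report Form". It states no time limit and no causality condition.

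**The concern.** Sections 7.1 and 7.2.2 both govern late SAEs, but they give the decision to different people. In Section 7.2.2 it is the investigator, and the word *only* makes that condition exclusive. In Section 7.1 the suspicion of the patient or the personal physician is enough.

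The stake is safety information. Safety and tolerability are the study's only objective (Sections 2.1 and 2.2), SAEs are a listed part of the primary assessment (Section 9.4), and there is no Data Monitoring Committee (Section 8.4). A patient who permanently stops LCZ696 leaves the study after a final visit, with further assessment only where an earlier adverse event needs follow-up (Section 5.5.9). It is a fair inference that a new event after that point reaches the site through unsolicited contact, which is the route Section 7.1 sets up. A site that applies Section 7.2.2 as written would then not pass on a serious event that someone outside the study team attributes to the drug, while a site that applies Section 7.1 would.

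**Working it through.** No formula applies, because the point depends on no sample size, error rate or event count. The check sets the rules side by side and runs each kind of late SAE through them.

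**The rules compared**

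| | Section 7.1 | Section 7.2.2 |
|---|---|---|
| Period | after the protocol observation period (not defined) | more than 30 days after the last dose |
| Whose suspicion counts | patient or personal physician | investigator only |
| Strength of duty | must | should only |

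**When both rules apply.** The Section 7.2.2 clock runs from the last administration of study treatment, not from a study day. If the observation period in Section 7.1 ends before the 30 days are over, the overlap is harmless, because every SAE is reportable in it. If it ends later, only Section 7.2.2 applies in between. The two triggers compete once both periods have ended.

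**Cases for an SAE in that period**

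1. The investigator suspects a relationship. Section 7.2.2 calls for a report. No conflict.
2. The patient or personal physician suspects a relationship and the investigator does not. Section 7.1 requires a report; Section 7.2.2 says not to make one. Direct conflict.
3. Nobody suspects a relationship and there is no pregnancy. Neither section calls for a report. No conflict.
4. The event is a recurrence, complication or progression of an earlier SAE. It is reportable at any time under Section 7.2.2. No conflict.
5. The event occurs during a pregnancy that began on treatment, and the investigator does not suspect a relationship. Read literally, Section 7.6 requires a report and Section 7.2.2 does not allow one. If the Section 7.6 sentence only names the form to use, there is no conflict.

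**Does the protocol settle case 2?** Sections 7.2.1, 7.3 and 7.7 all send sites to Section 7.2.2 for SAE reporting. No text says that Section 7.1 overrides Section 7.2.2, or that a Section 7.1 event must first pass the Section 7.2.2 condition. Case 2 is left open.

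**The case against.** The strongest defence is that a site has a workable course. Section 7.1 says must and Section 7.2.2 says should, so a careful site would report and depart only from the weaker instruction. One can also read Section 7.1 as passing serious events on to Section 7.2.2, the designated SAE reporting section. Both readings are possible and they soften the clash. They do not remove it, because they lead to opposite actions in case 2: the first produces a report and the second suppresses it.

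It is also fair to say that the planned tables hardly depend on this. SAP Section 9.7.1.6.1 assesses events during the study period, and most SAEs after the window would probably fall outside it. That stands: the effect is on what the sponsor learns, not on a planned estimate.

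On pregnancy the defence is stronger. Section 7.6 names the pregnancy form first and the SAE form afterwards, so its last sentence may be about forms only. The section already asks for on-treatment pregnancies to be reported and followed to outcome, including complications in mother and newborn and possible relationship to LCZ696, with no 30-day limit. A reader might infer that serious events late in an exposed pregnancy would be lost. The documents do not support that.

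A reader might also infer that the protocol permits sites to withhold late SAEs. It does not. An investigator who relied on Section 7.2.2 in case 2 would breach Section 7.1. The documents set protocol duties, and Section 7.2.2 refers reporting of suspected unexpected serious reactions to the European Directive or national requirements. The fault is an unresolved contradiction, not a permission.

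**Conclusion.** The contradiction is real and narrow. It covers a new SAE more than 30 days after the last dose, outside the protocol observation period, that the patient or personal physician attributes to LCZ696 and the investigator does not. For that event a site cannot follow both sections, and sites may report inconsistently.

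Its size in events cannot be derived. The documents give neither a rate of late SAEs nor a rate of disagreement about causality. A reader might take the planned enrolment as the number affected, but that is only the population to which the rules apply. No sample size or planned comparison changes.

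The conclusion assumes that *only* in Section 7.2.2 is meant as an exclusive condition and that the observation period in Section 7.1 eventually ends. The pregnancy question is secondary: an ambiguity about what one sentence in Section 7.6 is for. The point is worth correcting because safety is the study's sole objective and the correction is small.

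**What to change.** Amend the sentence in Section 7.2.2 on events after the window, for example: *An SAE with onset more than 30 days after the last dose is reported if the investigator, the patient or the patient's personal physician suspects a relationship to study treatment (see Section 7.1); the investigator's own causality assessment is recorded in every case.* Keep the term personal physician, so that the two sections name the same people.

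Add a cross-reference from Section 7.1 to Section 7.2.2, and define the protocol observation period in Section 7.1 as ending with the 30-day window, so that one rule takes over where the other stops.

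As a secondary change, state in Section 7.2.2 whether the Section 7.6 sentence on SAEs in pregnancy applies beyond the 30 days regardless of causality, or only names the form to use.

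The cost is a few lines in a protocol amendment and a few additional late SAE reports. Because the investigator's assessment is still recorded, reports made on another person's suspicion remain distinguishable. No analysis in the SAP needs to change.
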